7 STUDY TREATMENTS

7.1 Description of investigational medicinal products

The investigational medicinal products (IMPs) used in this study are CZP and PBO. These products will be supplied by the UCB Clinical Supply Unit. Drug and supplies will consist of the following:

Certolizumab pegol is supplied as a sterile, clear, colorless to slightly yellow liquid solution with a pH of approximately 4.7 in 1mL single use glass prefilled syringe (PFS) with a 25G ½-inch thin-wall needle for sc injection. Each syringe contains an extractable volume of 1mL at a

concentration of 200mg/mL of CZP in 10mM sodium acetate buffer and 125mM sodium chloride as a tonicity agent.

Placebo is supplied in a PFS with a 25G ½-inch thin-wall needle, containing an injectable volume of 1mL 0.9% saline for single use. Due to the difference in presentation and viscosity between CZP and PBO, special precautions will be taken in order to ensure maintained blinding of the study (unblinded/blinded site personnel and monitors).

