7.2 Treatments to be administered

The study medication is to be administered every 2 weeks by sc injections.

Study injections will be administered by study site staff. Suitable areas for sc injections are the upper arm, lateral abdominal wall, and upper outer thigh. During each dosing visit if 2 injections are being administered, each of the 2 injections should be administered at a separate injection site.

Injections should be administered with a minimum of 10 days between study injections. Each deviation less than these minimum timeframes must be discussed immediately with the Medical Monitor.

A pharmacy manual will be provided to each site containing instructions regarding drug preparation and dosing.

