2.3.1 Study design for subjects with moderate to severe chronic plaque PSO

2.3.1.1 Period 1: Screening

The Screening Period of 2 to 5 weeks will be used to confirm eligibility; obtain laboratory data; verify that the doses of nonsteroidal anti-inflammatory drugs (NSAIDs) and other pain relievers, such as acetaminophen, paracetamol, or mild opiates, if used to treat PsA are stable; and enable washout of any medications not permitted for use during the study.

2.3.1.2 Period 2: Initial Period - Week 0 to Week 16

Eligible subjects will be allocated to the following study treatments in a 2:2:1 ratio:

- CZP 400mg Q2W (n=50): CZP administered sc at the dose of CZP 400mg Q2W

- CZP 200mg Q2W (n=50): CZP administered sc at the dose of CZP 400mg at Weeks 0, 2, and 4, followed by CZP 200mg Q2W (starting at Week 6)
- PBO (n=25): PBO administered sc Q2W

Study treatments (including PBO) will be administered by dedicated, unblinded, trained site personnel at Baseline and Q2W thereafter to Week 14. Week 16 is the last study visit during this period.

2.3.1.3 Period 3: Maintenance Period - Week 16 to Week 52

The treatment received in Period 3 will be based on response to double-blind treatment at Week 16. All CZP and PBO treatments will be administered by dedicated, unblinded, trained site personnel at site visits, excluding the escape treatment.

Subjects who achieve a PASI50 response at Week 16 will continue therapy as follows:

- Subjects initially randomized to CZP 400mg Q2W will continue to receive CZP 400mg Q2W.
- Subjects initially randomized to CZP 200mg Q2W will be re-randomized (1:1) to receive either CZP 200mg Q2W or CZP 400mg Q4W (with PBO administered on alternate dosing weeks to maintain the blind).
- Subjects initially randomized to PBO will continue to receive PBO.

Subjects who do not achieve a PASI50 response at Week 16, 24, 32, or 40 will escape from double-blind treatment and receive treatment as follows:

- Escape treatment: Subjects entering the escape arm of the study will receive open-label CZP treatment (400mg Q2W as 3 loading doses followed by CZP 200mg Q2W). Subjects receiving open-label CZP 200mg Q2W in the escape arm and not achieving a PASI50 response will be allowed to have their dose increased to CZP 400mg Q2W, at the discretion of the Investigator. If, in the opinion of the Investigator, the subject is not receiving benefit (eg, a PASI50) at the CZP 400mg Q2W dose, the subject should be withdrawn from the study.

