7 MEASUREMENTS OF TREATMENT COMPLIANCE

Treatment compliance will utilize the number of administered injections and compare them to the scheduled expected number of injections. The sum of difference in number of injections between the actual and the expected injections will be summarized. In addition, the percent compliance will be calculated as:

Compliance (%) = $100 \times (\text{number of injections received} / \text{number of injections expected})$

and summarized using descriptive statistics for continuous data for the SS, FAS, CSS, and CFAS. Additionally, compliance will be summarized categorically based on whether subjects have compliance <80% or ≥80%.

The sum will be calculated for every visit of the considered period. Analyses according to the second approach will also be done for the SS, FAS, CSS, and CFAS.

The following compliance summaries will be performed:

- **Initial Period** – The first dose of the Initial Period is the first study dose at Baseline (Week 0) and the intended last dose is the Week 14 dose.
- **Maintenance Period** – The first dose of the Maintenance Period is the Week 16 dose and the intended last dose is the Week 50 dose. For the Interim Analysis, the intended last dose is the Week 22 dose.
- **Combined Initial and Maintenance Period** – The first dose of the Combined Initial and Maintenance Period is the first study dose at Baseline (Week 0) and the intended last dose is the Week 50 dose. For the Interim Analysis, the intended last dose is the Week 22 dose.

For visits where a subject is expected to receive study medication, see [Table 13–1](#). If a subject withdrew at a visit in which they were supposed to receive study treatment, then it will not be expected that the subject received an injection at that visit. In the case that a subject is lost to follow-up, and an early discontinuation visit is not conducted, then administration on last visit where the subject was available will be considered in the calculation of compliance.

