For subjects who die, if date of last administration of study medication + 14 days extends to a date beyond the date of death, then this calculation reverts to date of death – date of Week 16 administration of study medication + 1 day

For all subjects who do not escape during Maintenance:

- Date of last administration of study medication – date of first administration of study medication + 14 days is attributable to “All CZP”.

For subjects who die, if date of last administration of study medication + 14 days extends to a date beyond the date of death, then this calculation reverts to date of death – date of first administration of study medication + 1 day

For subjects who do switch to a different blinded treatment (or dose) at Week 16 and who do escape during Maintenance:

- Date of Week 16 administration of study medication – date of first administration of study medication is attributable to the original treatment.
- Date of first administration of open-label study medication – date of Week 16 administration of study medication is attributable to the treatment assigned at Week 16.
- Date of first administration of open-label study medication – date of first administration of blinded study medication is attributable to “All CZP”.

Number of days a dose was received

For subjects who discontinue on/prior to the Week 16 visit:

- Total number of dose days from Week 0 to last dose received (inclusive).

For subjects who escape at Week 16:

- Total number of dose days from Week 0 to last dose of blinded study medication received (inclusive).

For subjects who do not switch treatment (or dose) at Week 16 and who do not escape during Maintenance:

- Total number of dose days from Week 0 to last dose received (inclusive).

For subjects who do not switch treatment (or dose) at Week 16 and who do escape during Maintenance:

- Total number of dose days from Week 0 to last dose of blinded study medication received (inclusive)

For subjects who do switch to a different blinded treatment (or dose) at Week 16 and who do not escape during Maintenance:

- Total number of dose days from Week 0 to Week 14 (inclusive) is attributable to the original treatment.
- Total number of dose days from Week 16 up to Week 50 (inclusive) is attributable to the treatment assigned at Week 16.

For all subjects who do not escape during Maintenance:

- Total number of dose days on CZP from Week 0 up to Week 50 (inclusive) is attributable to “All CZP”.

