- Note that if the subject was initially randomized to CZP 200mg Q2W then the total number of dose days for CZP 200mg Q2W reverts to: total number of dose days from Week 0 to last open-label dose of CZP 200mg Q2W received (inclusive).
- Note that if the subject was initially randomized to CZP 400mg Q2W then the total number of dose days for CZP 400mg Q2W reverts to: total number of dose days from Week 0 to first open-label dose of CZP 200mg Q2W received (inclusive) + total number of dose days for open-label CZP 400mg Q2W.

For subjects who do switch to a different blinded treatment (or dose) at Week 16 and who do not escape during Maintenance:

- Total number of dose days from Week 0 to Week 14 (inclusive) is attributable to the original treatment (CZP 200mg Q2W).
- Total number of dose days from Week 16 up to Week 50 (inclusive) is attributable to the treatment assigned at Week 16 (CZP 400mg Q4W).
- Total number of dose days from Week 0 up to Week 50 (inclusive) is attributable to “All CZP”.

For subjects who do switch to a different blinded treatment (or dose) at Week 16 and who do escape to CZP 200mg Q2W during Maintenance but do not subsequently up-titrate to CZP 400mg Q2W:

- Total number of dose days from Week 0 to Week 14 (inclusive) + while on open-label CZP 200mg Q2W is attributable to the original treatment.
- Total number of dose days from Week 16 through last dose of blinded study medication (inclusive) is attributable to the treatment assigned at Week 16 (CZP 400mg Q4W).
- Total number of dose days from Week 0 through last dose received (inclusive) is attributable to “All CZP”.

For subjects who do switch to a different blinded treatment (or dose) at Week 16 and who do escape to CZP 200mg Q2W during Maintenance and who do subsequently up-titrate to CZP 400mg Q2W:

- Total number of dose days from Week 0 to Week 14 (inclusive) + while on open-label CZP 200mg Q2W is attributable to the original treatment.
- Total number of dose days from Week 16 through last dose of blinded study medication (inclusive) is attributable to the treatment assigned at Week 16 (CZP 400mg Q4W).

- Total number of dose days while on open-label CZP 400mg Q2W study medication (inclusive) is attributable to CZP 400mg Q2W.
- Total number of dose days from Week 0 through last dose received (inclusive) is attributable to “All CZP”.

For subjects who escape at Week 16 and do not subsequently up-titrate to CZP 400mg Q2W:

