- Total number of dose days from Week 0 to Week 14 (inclusive) is attributable to the original treatment.
- Total number of dose days while on open-label CZP 200mg Q2W study medication (inclusive) is attributable to CZP 200mg Q2W.
- If the subject was initially randomized to CZP 200mg Q2W then this algorithm reverts to: Total number of dose days from Week 0 to Week 50 (inclusive), all of which is attributable to CZP 200mg Q2W.
- Total number of dose days from Week 0 through last dose received (inclusive) is attributable to “All CZP”.

For subjects who escape at Week 16 and who do subsequently up-titrate to CZP 400mg Q2W:

- Total number of dose days from Week 0 to Week 14 (inclusive) is attributable to the original treatment.
- Total number of dose days while on open-label CZP 200mg Q2W study medication (inclusive) is attributable to CZP 200mg Q2W.
- Total number of dose days while on open-label CZP 400mg Q2W study medication (inclusive) is attributable to CZP 400mg Q2W.
- If the subject was initially randomized to CZP 200mg Q2W then this algorithm reverts to the sum of the total number of dose days while on CZP 200mg Q2W (either blinded or open-label).
- If the subject was initially randomized to CZP 400mg Q2W then this algorithm reverts to the sum of the total number of dose days while on CZP 400mg Q2W (either blinded or open-label).
- Total number of dose days from Week 0 through last dose received (inclusive) is attributable to “All CZP”.

Patient exposure days at risk

For subjects who discontinue on/prior to the Week 16 visit, use the minimum of the following:

- Date of last administration of study medication – date of first administration of study medication + 70 days
- Date of last clinical contact – date of first administration of study medication + 1 day

For subjects who die, this calculation reverts to date of death – date of first administration of study medication + 1 day

For subjects who do not switch treatment (or dose) at Week 16 and who do not escape during Maintenance, and who complete the Week 52 visit:

- Date of Week 50 administration of study medication – date of first administration of study medication + 70 days
- If the subject is missing their Week 50 injection date, then this calculation reverts to: Date of last administration of study medication – date of first administration of study medication + 70 days.

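### SAP 10.1.2 dose-day rules, as worded, count some placebo injection days as CZP and one day under two regimens

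*SAP*

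**What the plan says.** All the rules at issue are in SAP 10.1.2 (Final Analysis), under the number of days a dose was received.

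- **Subjects moved to CZP 400mg Q4W at Week 16.** SAP 2.3.1.3 describes the regimen as "CZP 400mg Q4W (with PBO administered on alternate dosing weeks to maintain the blind". In the combined-period rules (blinded plus open-label), for those who do not escape, "Total number of dose days from Week 16 up to Week 50 (inclusive) is attributable to the treatment assigned at Week 16", and all dose days from Week 0 to Week 50 go to All CZP. The blinded-only rules, for Maintenance and for the combined period, likewise give the assigned regimen every dose day from Week 16 to Week 50.
- **All CZP in the blinded-only combined table.** For all subjects who do not escape, "Total number of dose days on CZP from Week 0 up to Week 50 (inclusive) is attributable to" All CZP.
- **Subjects who escape at Week 16 (blinded plus open-label).** Weeks 0 to 14 go to the original treatment. In addition, "Total number of dose days from Week 0 through last dose received (inclusive) is attributable to" All CZP, whatever the original arm.
- **400mg Q2W subjects who escape after Week 16 and then up-titrate.** The 400mg Q2W count is the "total number of dose days from Week 0 to first open-label dose of CZP 200mg Q2W received (inclusive"), plus the open-label 400mg days. The open-label 200mg Q2W days go to 200mg Q2W.

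Protocol 7.1 states "The investigational medicinal products (IMPs) used in this study are CZP and PBO", and Protocol 7.2 states "The study medication is to be administered every 2 weeks by sc injections". The SAP never defines a dose day.

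**The concern.** This summary tells a reader how often each regimen was given. If placebo injections enter CZP columns, the Q4W column overstates how often CZP was delivered, and All CZP contains days on which no CZP was given. The placebo-escaper rule stands out because the same 8 days are assigned to placebo and to CZP within one table. Protocol 14.3 expects most placebo subjects to switch to CZP at Week 16, so this path is common.

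**Working it through.** The documents state no dose-day totals, so there is no figure to reproduce. The check counts visits on the 2-weekly grid for a subject who receives every planned dose.

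**Inputs.** Dosing every 2 weeks (Protocol 7.2). Last initial-period dose at Week 14, maintenance doses from Week 16 to Week 50 (SAP 7). Placebo on alternate weeks for Q4W (SAP 2.3.1.3).

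**Grid.**
- Weeks 0 to 14: 14/2 + 1 = 8 visits.
- Weeks 16 to 50: (50 − 16)/2 + 1 = 18 visits.
- Total: 8 + 18 = 26.
- Active Q4W visits in Weeks 16 to 50: 18/2 = 9. This holds whether the first active visit is Week 16 (16, 20, …, 48) or Week 18 (18, 22, …, 50).

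**(a) Placebo subject escaping at Week 16.**
- All CZP as worded: 8 + 18 = 26. Days with CZP: 18. Excess 8/18 = +44%.
- The duration rules for the same subjects start All CZP at the first CZP administration. For a completer that is (50 − 16) × 7 + 14 = 252 days, or 252/14 = 18 dosing intervals. The table would set 26 dose days against a duration that holds 18.
- Scale: 25 placebo subjects are planned. If a majority (13 to 25) escape at Week 16 after all 8 placebo doses, between 13 × 8 = 104 and 25 × 8 = 200 placebo days enter All CZP.

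**(b) Subject moved from 200mg Q2W to 400mg Q4W, no escape.**
- 400mg Q4W as worded: 18. Days with CZP: 9. Ratio 18/9 = 2.00.
- All CZP as worded (blinded plus open-label): 26. Days with CZP: 8 + 9 = 17. Ratio 26/17 = 1.53, or +53%.
- If the subject escapes later, the Q4W count stays doubled and the All CZP excess shrinks:

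| Escape at | Q4W days, worded / with CZP | All CZP, worded / with CZP |
|---|---|---|
| Week 24 | 4 / 2 | 26 / (8 + 2 + 14) = 24 |
| Week 32 | 8 / 4 | 26 / (8 + 4 + 10) = 22 |
| Week 40 | 12 / 6 | 26 / (8 + 6 + 6) = 20 |

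**(c) 400mg Q2W subject who escapes and up-titrates.** Take escape at Week 24 and, purely as an illustration, up-titration at Week 32.
- 400mg Q2W blinded part as worded: Weeks 0 to 24 inclusive = 13 days. Week 24 is the first open-label day and is also counted under 200mg Q2W.
- 200mg Q2W: Weeks 24 to 30 = 4. Open-label 400mg Q2W: Weeks 32 to 50 = 10.
- Sum as worded: 13 + 4 + 10 = 27, against 26 visits. Ending the blinded part at Week 22 gives 12 + 4 + 10 = 26.

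**The case against.** The strongest reply is that a dose day is undefined and that the SAP reports exposure by assigned regimen. Placebo on alternate weeks is part of the blinded Q4W regimen, and Q4W duration also runs to the last study medication of any kind plus 14 days. Counting every administration under the assigned regimen is then a convention that needs a footnote. This stands in part: (b) is what the wording literally produces, not an explicit instruction to count placebo as CZP, and a programmer could filter placebo out.

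It does not rescue (a). If a dose day is any injection day, or any day on the assigned regimen, a placebo subject's Weeks 0 to 14 are not CZP days. If it means CZP injections only, the placebo rows would be empty, while SAP 10.1.1 speaks of dose days attributable to placebo. Nor does it rescue (c), where one day falls under two regimens on any definition.

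A reader might also infer more than the documents support:

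- *That the words "on CZP" in the blinded-only All CZP rule prove an intention that was later lost.* That rule covers all non-escapers, including subjects who stay on placebo, so the words may only keep the placebo arm out.
- *That the Q4W column would match 200mg Q2W in the combined table.* It would not: a subject on 200mg Q2W throughout is counted from Week 0 and has 26 days, against 18. The two are equal only in the Maintenance-only blinded summary.
- *That compliance in SAP 7 has the same defect.* Injections received over injections expected measures adherence to the blinded schedule in every arm, and Protocol 7.7 likewise makes no active/placebo split. Changing it would be a preference.

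**Conclusion.** The point holds for the dose-day counts. The Week 16 placebo-escaper rule is wrong as written and contradicts the SAP's own duration rules: 26 against 18 All CZP days per completer, +44%. The Q4W rules, read literally, give 18 against 9 for the regimen and, in the blinded plus open-label table, 26 against 17 for All CZP. The up-titration rule adds one day per affected subject. These sizes assume every planned dose is given on the 2-weekly grid.

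A reader might infer that the safety rates are distorted. They are not: SAP 10.2 bases the exposure-adjusted incidence and event rates on time at risk, which is derived separately. The efficacy tests do not use dose days either. What changes is the reported dose-day exposure, which is reason enough to correct the text.

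**What to change.** In SAP 10.1.2:

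1. For CZP 400mg Q4W, the other CZP columns and All CZP, define a dose day as a day on which CZP was injected. Show blinding-placebo days for Q4W subjects separately.
2. For subjects who escape at Week 16, start the All CZP count at the first CZP dose, as the duration rules already do.
3. For 400mg Q2W subjects who escape and up-titrate, end the blinded 400mg count at the last blinded dose.
4. Word the parallel rules alike in the Maintenance blinded-only, combined blinded-only (non-escapers and later escapers) and combined blinded plus open-label parts.

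The cost is a wording change and a filter on the recorded dosing data by product given. The Q4W and All CZP dose-day figures become smaller. SAP 7 needs no change on this account.
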